8.3.2.2 Secondary Efficacy Analysis

Each secondary efficacy endpoint will be summarized by treatment group at each time point, as appropriate.

Following secondary endpoints will be analyzed:

- Change from baseline in ALP at Week 4, Week 8, Week 12 and Week 16 in Saroglitazar magnesium as compared to placebo.

Approved by: [name]	Protocol No. SARO.16.004 Version No.: 6.0
----------------------------------	--

- Change from baseline in lipid profile (TG, TC, HDL, LDL, and VLDL) at Week 4, Week 8, Week 12 and Week 16 in Saroglitzaz magnesium as compared to placebo.
- Change from baseline in liver biochemistries (GGT, ALT, AST, bilirubin and albumin) at Week 4, Week 8, Week 12 and Week 16 in Saroglitzaz magnesium as compared to placebo.
- Change from baseline in serum total bile acids at Week 4, Week 8, Week 12 and Week 16 in Saroglitzaz magnesium as compared to placebo.
- Change from baseline in 7α -hydroxy-4-cholesten-3-one (C4) and fibroblast growth factor 19 (FGF 19) at Week 16 in Saroglitzaz magnesium as compared to placebo.
- Proportion of patients with ALP improvement, i.e. 15%, 20%, 30%, 40% and normalization at Week 8 and Week 16.
- Change in QoL at Week 16 by using PBC40.
 - This instrument consists of 6 domain and 40 questions: symptoms, itch, cognition, emotion and social.
- Change from baseline in ALP in patients who are unable to tolerate UDCA at week 16 in Saroglitzaz 2 mg and 4 mg as compared to Placebo.
- Pharmacokinetics of Saroglitzaz.

The change from baseline will be determined as:

Change = (Post-baseline – Baseline)

Percent Change = (Post-baseline – Baseline) / Baseline * 100

Treatment effects will be estimated using the least-square mean, standard error and 95% confidence intervals from ANCOVA model with baseline value as covariate. Comparison will be done for Saroglitzaz magnesium (2 mg and 4 mg) and placebo using the difference in least-square means from the ANCOVA model. Proportion of patients with ALP

improvement, i.e., 15%, 20%, 30%, 40% and normalization at Week 8 and Week 16 will be presented as counts and percentages.

Descriptive statistics will be provided for each pharmacokinetic parameter.

The following pharmacokinetic parameters will be evaluated:

- i. Peak Plasma concentration (Cmax)
- ii. Time to reach peak Plasma concentration (Tmax)
- iii. Area under Plasma concentration vs. time curve till the last time point (AUC0-t)
- iv. Area under Plasma concentration vs. time curve extrapolated to the infinity (AUC0- ∞) after first dose
- v. Area under plasma concentration vs. time curve in a 24 h dosing interval (AU τ)
- vi. Elimination rate constant (λ_z)
- vii. Elimination half-life (t_{1/2})
- viii. Apparent Volume of distribution (Vd/F)
- ix. Apparent Clearance (CL/F)
- x. Minimal or Trough plasma concentration (C_{min}) -for last dose only
- xi. Accumulation index calculated as a ratio of AU τ (last dose)/AU τ (first dose)
- xii. Fluctuation index.

Above analyses will also be supported by simple summaries (n, mean, standard deviation, median, minimum and maximum) at each visit.

8.3.3 Safety Analysis

All safety analysis will be carried out on safety population. The frequency tabulations of abnormal clinical laboratory values for the parameter will be presented for each treatment group by visit. Summary statistics for clinical laboratory parameters, ECG, physical examination and vital signs will be presented for each treatment by visit.

All AEs seen during the study period will be listed. Incidence of all AEs reported during the study will be summarized using the Medical Dictionary for Regulatory Activities (MedDRA) (version 19 or higher) by treatment group, body system, frequency, severity, seriousness, and relationship to study drug and expectedness.

8.3.4 Baseline Characteristics

Demographic characteristics and Baseline Characteristics will be summarized by treatment, subject disposition, reasons for withdrawal or by any other variables as appropriate. Unless otherwise stated, all the continuous variables will be represented by n, mean, standard deviation, minimum, median and maximum. All the categorical variables will be presented as counts and percentages.

8.3.5 Interim Analysis

8.3.6 An interim analysis will be conducted when approximately 24th active randomized subject completes the study, that is Week 20 visit assessment. The purpose of this interim analysis is to assess the effect of Saroglitzaz Magnesium in PBC patients and to choose the optimal dose for planning the phase III study. The interim analysis will be performed with unmasking of specified individuals from the Sponsor who are not involved in the direct conduct of the trial. The study will continue until all planned subjects complete the study. Treatment masking of individual subjects will remain intact for all subjects, Investigators, and staff from the Sponsor who have contact with subjects or Investigators or those who are involved in the direct conduct of the study until all planned randomized subjects complete the study and the final database lock has occurred. Handling of Missing Data

Clarifications, wherever possible, will be obtained from the respective Investigator for any missing data or for any illegible entry, unused or unauthenticated data and this will be recorded in the data handling report before the final database lock.

Subjects who are discontinued from the study should be excluded from PP analysis set. Any randomized subjects who are discontinued from the study for any reason and have at least a post-baseline efficacy data should be included in the MITT analysis set using Last observation carried forward (LOCF) method. LOCF method will be used as an imputation method for the efficacy variables for MITT analysis.

8.4 RANDOMIZATION

Subjects will be randomly assigned in 1:1:1 treatment allocation ratio to Saroglitzaz magnesium 2 mg, Saroglitzaz magnesium 4 mg and placebo, respectively. The randomization schedule will be generated to ensure the treatment balance by using SAS® software (Version: 9.4 or higher; SAS Institute Inc., USA).

**Zydus Discovery
DMCC**

CLINICAL TRIAL PROTOCOL

Saroglitzaz Magnesium – Phase II

SARO.16.004

CONFIDENTIAL

PAGE 61 OF 82

8.5 DETERMINATION OF SAMPLE SIZE

This proof of concept study will include a total 36 subjects. Subject will be enrolled in 1:1:1 ratio to have 12 subjects in each arm i.e., Saroglitzaz magnesium 2 mg, Saroglitzaz magnesium 4 mg and placebo. Six patients in each group are planned for pharmacokinetic assessment therefore a total of 18 patients will be included. Additional patients may be enrolled into the study to ensure the pharmacokinetic assessment is performed on at least 6 completed patients in each treatment arm. Additional patients will be enrolled if the dropout rate is more than 20%.

Approved by:
[name]

Protocol No. SARO.16.004
Version No.: 6.0

9 ADMINISTRATIVE MATTERS

The trial will be carried out in compliance with the protocol, in accordance with the ICH Harmonised Tripartite Guideline for GCP and in accordance with applicable regulatory requirements.

9.1 ETHICS

9.1.1 Institutional Committee Review and Communications

The trial will not be initiated before the protocol and informed consent and subject information form have been reviewed and have received approval / favorable opinion from the USFDA-registered IEC/IRB. Should a protocol amendment be written that requires IEC/IRB approval, the changes in the protocol will not be instituted until the amendment and revised informed consent (if appropriate) has been reviewed and received approval / favorable opinion from the IEC/IRB. A protocol amendment intended to eliminate an apparent immediate hazard to subjects may be implemented immediately providing that the appropriate regulatory authorities and IEC/IRB are notified as soon as possible and an approval is requested. Protocol amendments only for logistical or administrative changes may be implemented immediately; however, both the IRB/IEC and the Regulatory Authority will be notified as soon as possible.

The constitution of the IEC/IRB must comply with the requirements of the US Code of Federal Regulations. A list of the IEC/IRB members, with names and qualifications, will be requested. If such a list is unavailable, the Investigator must provide the name and address of the central IEC/IRB along with a statement from the IEC/IRB that it is organised according to GCP and the applicable laws and regulations. The IEC/IRB must also perform all duties outlined by the requirements of the regulatory agencies.

9.1.2 Informed Consent and Subject Information

Prior to subject participation in the trial, written informed consent will be obtained from each subject (or the subject's legally accepted representative) according to the regulatory and legal requirements of the participating country. Each signature must be dated by each signatory and the informed consent and any additional subject information form retained by

**Zydus Discovery
DMCC**

CLINICAL TRIAL PROTOCOL

Saroglitazar Magnesium – Phase II

SARO.16.004

CONFIDENTIAL

PAGE 63 OF 82

the Investigator as part of the study records. A signed copy of the IEC/IRB approved informed consent and any additional subject information must be given to each subject or the subject's legally authorised representative.

The subject must be informed that his / her medical records may be examined by authorised monitors or Clinical Quality Assurance auditors appointed by the Sponsor, by appropriate IEC / IRB members and by inspectors from regulatory authorities.

Should a protocol amendment be made, the subject consent form and subject information form may need to be revised to reflect the changes to the protocol. It is the responsibility of the Investigator to ensure that an amended consent form is reviewed and received approval from the IEC/IRB, and to further ensure that it is signed by all subjects subsequently entered in the trial and those currently in the trial, if affected by the amendment.

9.2 DATA MANAGEMENT AND RECORDKEEPING

9.2.1 Drug Accountability

Drug supplies, which will be provided by the Sponsor, must be kept in a secure, limited access storage area under the storage conditions defined by the Sponsor. A temperature log must be maintained to make certain that the drug supplies are stored at the correct temperature.

The Investigator and/or pharmacist must maintain records of the product's delivery to the trial site, the inventory at the site, the use by each subject, and the return to the Sponsor or alternative disposition of unused product(s). These records will include dates, quantities, batch/serial numbers, expiration dates (if applicable), and the unique code numbers assigned to the IP(s) and trial subjects. Investigators will maintain records that document adequately that the subjects were provided the doses specified by the protocol and reconcile all IP(s) received from the Sponsor.

After the study has been completed, the PI must account for all study drug used, unused and partially used. All study drugs will be adequately destroyed at the site (per site's SOPs) or returned to the Sponsor (or designee). Unused drug supplies will be destroyed at the site

Approved by:
[name]

Protocol No. SARO.16.004
Version No.: 6.0

after approval for the same by the Sponsor. No study drug will be destroyed or returned until drug accountability has been performed by the study monitor.

9.2.2 Patient Card

Upon enrolment in the study, patients will receive a patient card to be carried at all times.

The patient card will state that the patient is participating in a clinical research study, type of treatment, number of treatment packs received, and contact details in case of an SAE.

9.2.3 Data Management

9.2.3.1 Data Handling

Data will be recorded at the site on eCRFs and reviewed by the clinical research associate (CRA) during monitoring visits. The CRAs will verify data recorded in the electronic data capture (EDC) system with source documents. All corrections or changes made to any study data must be appropriately tracked in an audit trail in the EDC system. An eCRF will be considered complete when all missing, incorrect, and/or inconsistent data has been accounted for.

9.2.3.2 Computer Systems

Data will be processed using a validated computer system conforming to regulatory requirements.

9.2.3.3 Data Entry

Data must be recorded using the EDC system as the study is in progress. All site personnel must log into the system using their secure user name and password in order to enter, review, or correct study data. These procedures must comply with Title 21 of the Code of Federal Regulations (21 CFR Part 11) and other appropriate international regulations. All passwords will be strictly confidential.

9.2.3.4 Medical Information Coding

For medical information, the following thesauri will be used:

- Latest version of MedDRA for adverse events and medical history, and

- WHO Drug Dictionary for prior and concomitant medications.

9.2.3.5 Data Validation

Validation checks programmed within the EDC system, as well as supplemental validation performed via review of the downloaded data, will be applied to the data in order to ensure accurate, consistent, and reliable data. Data identified as erroneous, or data that are missing, will be referred to the investigative site for resolution through data queries.

The eCRFs must be reviewed and electronically signed by the Investigator.

9.2.4 Source documents

Source documents provide evidence for the existence of the subject and substantiate the integrity of the data collected. Source documents are filed at the Investigator's site. Data reported on the eCRFs that are derived from source documents (SDs) must be consistent with the SDs or the discrepancies must be explained.

The Investigator may need to request previous medical records or transfer records, depending on the trial; also current medical records – not just shadow charts – must be available.

The following data to be reported on the eCRF should be included and derived from the source documents:

- Subject identification (subject number, gender, date of birth/age)
- Subject participation in the trial (substance, trial number, patient number, date informed consent given)
- Dates of subject's visits
- Medical history
- Medication history
- AEs (onset and end)
- SAEs (onset and end)
- Originals or copies of laboratory results: All laboratory reports must be reviewed by the Investigator and/or his/her designee; any abnormal findings should be addressed.

**Zydus Discovery
DMCC**

CLINICAL TRIAL PROTOCOL

Saroglitazar Magnesium – Phase II

SARO.16.004

CONFIDENTIAL

PAGE 66 OF 82

- Conclusion of subject's participation in the trial.

9.2.5 Direct access to source data / documents

The Investigator/ institution will permit trial-related monitoring, audits, IRB / IEC review and regulatory inspection, providing direct access to all related source data / documents. Case report forms and all SDs, including progress notes and copies of laboratory and medical test results must be available at all times for review by the Sponsor's clinical trial monitor and inspection by health authorities (e.g., FDA, or other applicable regulatory authorities). The on-site monitor will review all eCRFs, and written informed consents. The accuracy of the data will be verified by reviewing the documents described in Section 9.2.4.

9.2.6 Trial Monitoring

It is the responsibility of the Investigator to ensure that the study is conducted in accordance with the protocol, ICH GCP, and applicable regulatory requirements, and that valid data are entered into the eCRFs.

To achieve this objective, the study monitor's duties are to aid the Investigator and, at the same time, the Sponsor in the maintenance of complete, legible, well organized and easily retrievable data. Before the enrolment of any patient in this study, the Sponsor or their designee will review with the Investigator and site personnel the following documents: protocol, Investigator's Brochure, eCRFs and procedures for their completion, informed consent process, and the procedure for reporting SAEs.

The Investigator will permit the Sponsor or their designee to monitor the study as frequently as deemed necessary to determine that data recording and protocol adherence are satisfactory. During the monitoring visits, information recorded on the eCRFs will be verified against source documents and requests for clarification or correction may be made. After the eCRF data is entered by the site, the CRA will review the data for safety information, completeness, accuracy, and logical consistency. Computer programs that identify data inconsistencies may be used to help monitor the clinical study. If necessary, requests for clarification or correction will be sent to Investigators. The Investigator and his/her staff will be expected to cooperate with the monitor and provide any missing information, whenever possible.

Approved by:
[name]

Protocol No. SARO.16.004
Version No.: 6.0

9.3 QUALITY ASSURANCE AUDIT

A quality assurance audit of this trial may be conducted by the Sponsor or Sponsor's designees. The quality assurance auditor will have access to all medical records, the Investigator's trial related files and correspondence, and the informed consent documentation that is relevant to this clinical trial.

9.4 PROCEDURES

9.4.1 Adverse Events

All AEs occurring during the course of the clinical trial (i.e., from signing the informed consent onwards) will be collected, documented and reported to the Sponsor by the Investigator according to the specific definitions and instructions detailed in this section.

An AE is defined as any untoward medical occurrence in a clinical investigation subject administered a pharmaceutical product and which does not necessarily have to have a causal relationship with this treatment.

Any medical condition already present at screening should not be reported as an adverse event unless the medical condition or signs or symptoms present at baseline changes in severity or seriousness at any time during the study. In this case, it should be reported as an adverse event.

Clinically significant abnormal laboratory or other examination (e.g. electrocardiogram) findings that are detected during the study or are present at screening and significantly worsen during the study should be reported as AEs. The investigator will exercise his or her medical and scientific judgment in deciding whether an abnormal laboratory finding or other abnormal assessment is clinically significant. Clinically significant abnormal laboratory values occurring during the clinical study will be followed until repeat tests return to normal, stabilize, or are no longer clinically significant. Any abnormal test that is determined to be an error does not require reporting as an AE.

9.4.2 Serious Adverse Event

A serious adverse event is any adverse event occurring at any dose or during any use of Sponsor's product that:

- Results in death;
- Is life threatening;
- Results in persistent or significant disability/incapacity;
- Results in inpatient hospitalization or prolongs an existing inpatient hospitalization;
- Is a congenital anomaly/birth defect;
- Is another important medical event that may not result in death, be life-threatening, or require hospitalization may be considered serious when, based upon appropriate medical judgment, they may jeopardize the patient or subject and may require medical or surgical intervention to prevent one of the outcomes listed above.

Serious Adverse Event Reporting-Procedures for Investigators:

Initial Reports:

Any serious adverse event, or follow-up to a serious adverse event, including death due to any cause that occurs to any subject from the time the consent is signed through 7 days following cessation of treatment, whether or not related to the Sponsor's product, must be reported to the Sponsor within 24 hours of the knowledge of the occurrence to investigational site.

Additionally, any serious adverse event, considered by an Investigator who is a qualified physician to be related to the Sponsor's product that is brought to the attention of the Investigator at any time outside of the time period specified in the previous paragraph also must be reported immediately to the Sponsor.

To report the SAE, complete the SAE form electronically in the electronic data capture (EDC) system for the study. When the form is completed, CRO/Sponsor Safety personnel

**Zydus Discovery
DMCC**

CLINICAL TRIAL PROTOCOL

Saroglitazar Magnesium – Phase II

SARO.16.004

CONFIDENTIAL

PAGE 69 OF 82

will be notified electronically and will retrieve the form. If the event meets serious criteria and it is not possible to access the EDC system, send an email to CRO/Sponsor or call the CRO/Sponsor SAE hotline (phone number listed below), and email the completed paper SAE form to CRO/Sponsor (email listed below) within 24 hours of awareness. When the EDC system becomes available, the SAE information must be entered within 24 hours of the system becoming available.

Safety Contact Information:

[name] [name]

[REDACTED]

Follow-Up Reports

All subjects with serious adverse events must be followed up for outcome. Within 24 hours of receipt of follow-up information, the investigator must update the SAE form electronically in the EDC system for the study and submit any supporting documentation (e.g., subject discharge summary or autopsy reports) to CRO/Sponsor Clinical Safety via fax or e-mail. If it is not possible to access the EDC system, refer to the procedures outlined above for initial reporting of SAEs.

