After screening, the eligible patients will be randomly assigned to one of the following treatment groups in addition to their ongoing treatment with UDCA (Patients unable to tolerate UDCA will receive only the investigational medicinal products) i.e., Saroglitzaz magnesium 2 mg, Saroglitzaz magnesium 4 mg, or placebo. Vital signs measurements, weight measurements, physical examination, and laboratory examination will be performed as mentioned in Table 1. Concomitant medications will be recorded. AEs will be noted, if any. Urine pregnancy test will be performed for women of childbearing potential. Subjects will undergo cardiac evaluation (ECG). A 4-week supply of study medication (one bottle) will be dispensed. Baseline quality of life assessment will be performed.

- **Visit 3.1 (Week 2±3 Days)**

Patient will visit study site at 2 weeks after randomization visit for LFTs. The LFTs will be performed at local laboratory.

- **Visit 4 (Week 4±3 Days), Visit 5 (Week 8±3 Days) and Visit 6 (Week 12±3 Days)**

Subjects will be undergo a physical examination and laboratory parameters (safety and efficacy) will be assessed as per Table 1. Vitals signs, body weight will be recorded.

AEs, if any, will be noted. Urine pregnancy test will be performed for women of childbearing potential. Concomitant medications will be recorded. Medication compliance will be checked. Medication will be dispensed on each visit for next 4 weeks.

- **End-of-treatment Visit 7 (Week 16±3 Days)**

Subjects undergo physical examination and laboratory parameters (safety and efficacy) will be assessed as per Table 1. Vitals signs and weight will be recorded. AEs will be noted, if any. Subjects will undergo cardiac (ECG) evaluation. Pregnancy test will be performed for all women of childbearing potential. Concomitant medications will be recorded. Medication compliance will be checked.

- **Safety follow-up Visit 8 End of Study (Week 20±3 Days)**

A safety follow-up visit will be performed 4 weeks after End-of-treatment Visit. Patients clinical examination and safety lab assessment will be performed as per Table 1.

Unscheduled visits- will be allowed any time during the study for assessment and management of AEs and any concurrent clinical conditions. Unscheduled visits shall be captured in the CRF.

- If further investigations are required in case of any AE, Investigator will assess the AE and take necessary action, if required.

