8.3.2 Adverse Events

The applicable definition of an Adverse Event (AE) is in the study protocol. All AEs occurring from when a patient signs informed consent to when a patient exits the study will be accounted for in the reporting. Analysis and presentation of AEs occurring during the screening period will be separated from those occurring during the investigational period where a comparative evaluation of treatment-emergent AEs is intended. A treatment-emergent AE is an event not present prior to exposure to investigational product or any pre-existing event that worsens following exposure to investigational product. The period for treatment-emergent AE analysis starts from the first exposure to the investigational product until the patient exits the study.

Descriptive summaries (frequencies and percentages) for specific AEs will be presented by system organ class and preferred term according to the Medical Dictionary for Regulatory Activities (MedDRA Version 19.1) dictionary by treatment group and overall. In addition to an overall presentation of all AEs, reports will be generated for special classes of AEs such as investigational product related AEs, serious AEs, Maximum severity and AEs resulting in treatment discontinuation by treatment group. These reports will be supported by individual patient listings, as necessary.

Document Title:	Statistical Analysis Plan		
Version Number:	2.0	Date:	11 Nov 2019
Protocol Number:	SARO.16.004	Sponsor Name:	Zydus Discovery DMCC

Adverse events will be counted by the number of events as well as the number of subjects. For the summaries which count the number of patients by treatment group and overall, multiple AEs with the same MedDRA preferred term within the same patient will only be counted once.

Descriptive summaries (frequencies and percentages) for number of subjects experiencing AEs will also be presented.

Only patient listings will be provided for AEs that occur after signing informed consent but prior to exposure to investigational product. These listings will comprise all events occurring during this period in any patient who consented to participate in the study.

These listings will at least contain but not limited to information such as onset and resolution times, maximum severity, causal relationship to study treatment and action taken.

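### 24-hour any-cause SAE reporting ends 7 days after treatment, about three weeks before safety follow-up ends, so late SAEs judged unrelated have no stated expedited deadline

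*Protocol*

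**What the plan says.** Protocol 9.4.2 sets the any-cause rule. An SAE, including a death, that occurs "from the time the consent is signed through 7 days following cessation of treatment" "must be reported to the Sponsor within 24 hours of the knowledge of the occurrence to investigational site". The next paragraph adds that an SAE the investigator considers related and learns of "at any time outside of the time period specified in the previous paragraph also must be reported immediately to the Sponsor".

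Other parts of the plan run longer:

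- Protocol 7.2: "A safety follow-up visit will be performed 4 weeks after End-of-treatment Visit".
- Protocol 9.4.1: "All AEs occurring during the course of the clinical trial (i.e., from signing the informed consent onwards) will be collected". No deadline is given there.
- Protocol 9.4.6: pregnancies are reportable up to 4 weeks ±3 days after the treatment period.
- SAP 8.3.2: "The period for treatment-emergent AE analysis starts from the first exposure to the investigational product until the patient exits the study".

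Two further sections bear on timing. Protocol 6.2 asks that the sponsor be notified of all AEs, but refers SAE timelines back to the adverse event section, so it sets no deadline of its own. Protocol 9.4.4 requires Events of Clinical Interest to be reported within 24 hours, using the 9.4.2 procedures.

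**The concern.** The protocol keeps patients under safety observation for 4 weeks after treatment, and the SAP attributes events in that time to the treatment-emergent period. Yet the any-cause 24-hour rule lapses after the first week. From then on, prompt reporting depends on one blinded investigator's yes/no judgement of causality.

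That judgement is hard in this population. Table 4 in Protocol 9.4.3 lists underlying disease among the alternative explanations to be weighed, and every patient has primary biliary cholangitis. A late hepatic SAE can plausibly be put down to the disease, and it then loses its deadline.

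Oversight is what could suffer. Protocol 7.6 has a Data Monitoring Committee review AEs and liver-related events regularly. Item (g) in Protocol 4.4.1 allows the trial to be stopped, or unblinded safety data to be evaluated, if more than 3 patients have a grade 3 or higher event in the same category, and that count does not depend on causality. With about 24 patients planned on active drug (12 + 12), a single SAE that arrives late can affect when such a count is recognised, possibly while other patients are still being dosed.

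**Working it through.** The plan gives no figure for this gap, so there is none to reproduce. As a check on the calendar, 6 weeks of screening + 16 of treatment + 4 of follow-up = 26 weeks, which agrees with the study duration in Protocol 7.1.

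**Inputs**

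| Item | End point after treatment | Source |
|---|---|---|
| Any-cause SAE, 24-hour rule | 7 days | Protocol 9.4.2 |
| Related SAE, immediate rule | none | Protocol 9.4.2 |
| Safety follow-up visit | 28 days (25 to 31) | Protocol 7.1, 7.2 |
| Pregnancy reporting | 4 weeks ±3 days | Protocol 9.4.6 |
| Treatment-emergent AE period | study exit | SAP 8.3.2 |

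**Size of the gap.** Let F be the number of follow-up days. Days beyond the any-cause rule = F − 7, and the share is (F − 7)/F.

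- F = 28: 28 − 7 = 21 days; 21/28 = 75%.
- F = 25 (visit 3 days early): 18 days; 18/25 = 72%.
- F = 31 (visit 3 days late): 24 days; 24/31 = 77%.

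For scale, a completer's treatment-emergent period is 16 × 7 + 28 = 140 days, and 21/140 = 15%.

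**Which events the gap touches (F = 28)**

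| Type of SAE | Follow-up days without a stated prompt deadline |
|---|---|
| Judged related | 0 |
| Event of Clinical Interest | 0, if 9.4.4 is read as having no end date |
| Judged unrelated and not an Event of Clinical Interest | 21 |

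**How far the Events of Clinical Interest rule helps.** The hepatic criterion in 9.4.4 needs ALT or AST at least 3×ULN, bilirubin at least 2×ULN and, at the same time, ALP below 2×ULN. Entry requires ALP of at least 1.67×ULN at two screening visits (Protocol 4.2). A patient whose ALP is 2×ULN or more at the time of the event cannot qualify, whatever the other values. The documents do not show how many patients that would be, since ALP may fall on treatment. The criterion also leaves out non-hepatic SAEs and deaths.

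**The case against.** The strongest reply is that these windows serve different purposes and need not be equal. Expedited reporting, AE collection, pregnancy reporting and the analysis period can each have their own end date, and 9.4.1 says AEs are reported under the specific instructions of its section, which include 9.4.2. This stands: the plan does not contradict itself. The elimination data that might support 7 days could also lie in Protocol 2.3, whose content is not visible in the public copy. One can say that 9.4.2 states no reason for the 7 days, not that no reason exists.

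Stronger readings are tempting, but the documents do not support them:

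- *Most of follow-up has no prompt reporting at all.* The related-SAE rule has no end date, and 9.4.4 adds a 24-hour duty that does not depend on causality.
- *Late SAEs are lost to the analysis.* They are not. Protocol 9.4.1 and 6.2 have all AEs collected and notified to the sponsor, and SAP 8.3.2 counts them to study exit.
- *Safety and clinical records would fail to agree.* The documents describe no separate safety database; SAE forms are completed in the study's electronic data capture system.
- *A patient who stops early has a far longer gap, lasting to Week 20.* The plan does not describe continued off-drug follow-up to Week 20. Early discontinuation leads to the End-of-treatment procedures, and Visit 8 is timed from that visit, which gives a similar gap of about three weeks.
- *There can be no more than 24 patients on active drug.* Twenty-four is the planned number; Protocol 4.1 allows additional enrolment.

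It is also fair to say that the review trigger in 4.4.1 counts grades and laboratory criteria, not SAE forms. An expedited report affects when a count is noticed, not whether it is eventually made.

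**Conclusion.** The concern holds as a narrow point about timeliness. For about three of the four weeks of safety follow-up (21 of 28 days, 75%; 72% to 77% across the visit window), an SAE judged unrelated that is not an Event of Clinical Interest has no stated expedited deadline. This includes deaths. No analysis result or population is affected. What is at stake is how soon the sponsor and the Data Monitoring Committee learn of such an event in a small trial.

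The size rests on two assumptions: that treatment ceases at the End-of-treatment Visit, and that 9.4.4 carries no end date. If the last dose precedes that visit, the gap lengthens by the same number of days. If 9.4.4 inherits the 7-day limit from 9.4.2, Events of Clinical Interest judged unrelated fall into the gap too. Aligning the windows is a worthwhile, inexpensive improvement and not the repair of a serious defect.

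**What to change.** In Protocol 9.4.2, move the end of the any-cause 24-hour SAE window from 7 days after cessation of treatment to the safety follow-up/end-of-study visit (Visit 8). This matches Protocol 7.2 and SAP 8.3.2 and brings the window into line with pregnancy reporting in 9.4.6. Keep the paragraph on related SAEs unchanged, so that they stay reportable at any time. State which date closes the window for a patient who does not attend Visit 8. If the sponsor prefers to keep 7 days, 9.4.2 should give the reason.

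The cost is one line in an amendment and a few more expedited SAE forms for sites and safety staff. With the change, the 21-day gap for a completer falls to 0 days.
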